6.6.2. Azacitidine

For azacitidine dose modification, refer to the local package insert (or SPC) or IP Manual.

6.7. Intervention After the End of the Study

No intervention will be provided to study participants at the end of the study.

7. DISCONTINUATION OF STUDY INTERVENTION AND PARTICIPANT DISCONTINUATION/WITHDRAWAL

7.1. Discontinuation of Study Intervention

In rare instances, it may be necessary for a participant to permanently discontinue study intervention (definitive discontinuation). Reasons for definitive discontinuation of study intervention may include the following:

- Objective disease progression or relapse
- Participant refusal
- Consent withdrawal
- Unacceptable toxicity
- Pregnancy
- Initiation of another anti-cancer treatment

If study intervention is definitively discontinued, the participant will not remain in the study for further evaluation. See the [SoA](#) for data to be collected at the time of discontinuation of study intervention.

Note that discontinuation of study intervention does not represent withdrawal from the study. If study intervention is definitively discontinued, the participant will remain in the study to be evaluated for 28 calendar days after the last dose of study treatment administration. See the [SoA](#) for data to be collected at the time of discontinuation of study intervention and follow-up for any further evaluations that need to be completed.

In the event of discontinuation of study intervention, it must be documented on the appropriate CRF/in the medical records whether the participant is discontinuing further receipt of study intervention or also from study procedures, posttreatment study follow-up, and/or future collection of additional information.

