Pregnancy test/Contraception check	X	X	X		
 Male participants with female partner of childbearing potential and female participants who are of childbearing potential will need to affirm that they meet the criteria for correct use of the selected methods of contraception. In addition, the investigator or his or her designee will instruct the participant to call immediately if the selected contraception method is discontinued, or if pregnancy is known or suspected in the participant or the participant's partner. Refer to Appendix 4 for contraceptive guidance. Appropriate contraception usage for at least 180 days after the last dose of study intervention is to be confirmed
Disease Assessment	As per Standard of Care at the Study Site				
Concomitant treatment(s)		X	X	X	

a. Study participants will be followed (can be by telephone) for 28 calendar days after the last administration of study treatment to capture any AE/SAEs. There will be no further follow-up required after the 28-day safety reporting period.

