4.4. End of Study Definition

A participant is considered to have completed the study if he/she has completed all phases of the study, including the 28-day safety follow-up period.

The end of this Study is defined as when all participants have discontinued from study treatment and have completed the Safety Follow-up Period. The safety follow-up period is defined as 28 days after last dose of last study drug. The study may also be terminated at any time at the discretion of the Sponsor.

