7.2.1. Withdrawal of Consent

Participants who request to discontinue receipt of study intervention will remain in the study and must continue to be followed for protocol-specified follow-up procedures. The only exception to this is when a participant specifically withdraws consent for any further contact with him or her or persons previously authorized by the participant to provide this information. Participants should notify the investigator in writing of the decision to withdraw consent from future follow-up, whenever possible. The withdrawal of consent should be explained in detail in the medical records by the investigator, as to whether the withdrawal is only from further receipt of study intervention or also from study procedures and/or posttreatment study follow-up, and entered on the appropriate CRF page. In the event that vital status (whether the participant is alive or dead) is being measured, publicly available information should be used to determine vital status only as appropriately directed in accordance with local law.

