8.3.1. Time Period and Frequency for Collecting AE and SAE Information

The time period for actively eliciting and collecting AEs and SAEs (“active collection period”) for each participant begins from the time the participant provides informed consent, which is obtained before the participant’s participation in the study (ie, before undergoing any study-related procedure and/or receiving study intervention), through and including a minimum of 28 calendar days after the last administration of the study intervention.

Follow-up by the investigator continues throughout and after the active collection period and until the AE or SAE or its sequelae resolve or stabilize at a level acceptable to the investigator and Pfizer concurs with that assessment.

For participants who are screen failures, the active collection period ends when screen failure status is determined.

If the participant withdraws from the study and also withdraws consent for the collection of future information, the active collection period ends when consent is withdrawn.

If a participant definitively discontinues or temporarily discontinues study intervention because of an AE or SAE, the AE or SAE must be recorded on the CRF and the SAE reported using the CT SAE Report Form.

Investigators are not obligated to actively seek AEs or SAEs after the participant has concluded study participation. However, if the investigator learns of any SAE, including a death, at any time after a participant has completed the study, and he/she considers the event to be reasonably related to the study intervention, the investigator must promptly report the SAE to Pfizer using the CT SAE Report Form.

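### Protocol 7.1 says in consecutive paragraphs that a participant who stops study intervention will not, and will, stay in the study; the first statement conflicts with the 28-day AE/SAE follow-up required elsewhere

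*Protocol*

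**What the plan says.** Protocol 7.1 lists possible reasons for permanent discontinuation of study intervention. It then states: "If study intervention is definitively discontinued, the participant will not remain in the study for further evaluation". The same paragraph refers the reader to the Schedule of Activities for the data to collect at discontinuation.

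The following paragraph opens: "Note that discontinuation of study intervention does not represent withdrawal from the study". It continues: "If study intervention is definitively discontinued, the participant will remain in the study to be evaluated for 28 calendar days after the last dose".

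The rest of the protocol sides with the second paragraph. Footnote a of the Schedule of Activities has participants followed "for 28 calendar days after the last administration of study treatment to capture any AE/SAEs". Under 4.4, a participant completes the study on having "has completed all phases of the study, including the 28-day safety follow-up period". Section 7.2.1 says that those who ask to stop treatment "will remain in the study and must continue to be followed for protocol-specified follow-up procedures". Section 8.3.1 runs active AE/SAE collection from consent "through and including a minimum of 28 calendar days after the last administration of the study intervention". Protocol 3 names AEs and SAEs as the only endpoint.

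**The concern.** The two statements in 7.1 share one condition and reach opposite outcomes. Read literally, the first ends evaluation once the discontinuation data have been collected, and the 28 days that follow go unobserved.

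Those days belong to the endpoint. The summaries in Protocol 9.4.1 and SAP 6.3.1 count participants in the safety analysis set who have treatment-emergent events, and the window for those events closes 28 days after the last dose. If a site stopped looking early, the participant would stay in the denominator while any later event was missing from the numerator. SAP 5.3 evaluates data as observed, so a follow-up that was never done would look the same as a follow-up with no events. Any error would lower the event frequencies.

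SAE reporting is exposed in the same way. That includes the protocol-specified reporting of Grade 3 or 4 mQTcF prolongation in 8.3.11, which extends over the same 28 days.

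**Working it through.** There is no design figure to reproduce: Protocol 9.1 and 9.2 state that hypotheses and sample size do not apply. The check sets the passages side by side.

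1. **Trigger.** Both statements in 7.1 begin from definitive discontinuation of study intervention. Neither is limited to a cohort, a reason for stopping or a time after stopping. Both are current Amendment 6 text, not amendment history.

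2. **Outcome.** The first says the participant does not stay for evaluation. The second says the participant stays for 28 calendar days after the last dose. Both cannot be followed.

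3. **Collection and follow-up text elsewhere.**
   - Schedule of Activities: AE monitoring is marked in the 1-month safety follow-up column, and footnote a sets 28 days for AEs and SAEs.
   - Synopsis (1.1) and 2.1: the 28-day safety follow-up is called mandatory.
   - 4.4: the 28-day period is part of completing the study, and the study ends only when everyone has stopped treatment and finished it.
   - 7.2.1: a request to stop treatment does not end follow-up.
   - 8.2.5: follow-up lasts 28 calendar days, and none is required after that.
   - 8.3.1: active collection lasts at least 28 calendar days after the last administration. 8.3.1.1 and 8.3.1.2 apply that period.
   - 8.3.11: the mQTcF SAE requirement runs to 28 days after the last dose.

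4. **Analysis windows.** Protocol 9.4.1 and SAP 3.3 start the window at different points (Amendment 6 consent and first non-zero dose respectively), but both end it 28 days after the last dose. The end is what matters here, and it agrees with the second paragraph of 7.1.

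5. **Planned early ends to collection.** For a participant who withdraws from the study and also withdraws consent for future information, 8.3.1 says "the active collection period ends when consent is withdrawn". Under 8.3.1.2, nonserious AE recording stops when a new anticancer therapy starts, while SAEs continue to be recorded. These are deliberate, stated limits. Neither supports the general statement in the first sentence of 7.1, and neither is part of this point.

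6. **Two neighbouring passages.**
   - 7.2 lists progression, pregnancy and unacceptable toxicity among possible reasons for leaving the study, and says the participant then leaves both intervention and study. The same three reasons appear in 7.1 for stopping treatment.
   - 8.2.5 describes the purpose of follow-up as capturing SAEs and AEs that led to permanent discontinuation. That is narrower than footnote a of the Schedule of Activities.

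The 28-day length is the same wherever it is stated. The first sentence of 7.1 is the outlier.

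**The case against.** The strongest reply is that the conflict is close to resolved where it stands. The next paragraph of 7.1 corrects the sentence, and the sentence's own paragraph sends the reader to the Schedule of Activities, which requires the follow-up. To under-collect, a site would have to overlook both, and also 4.4, 8.2.5 and 8.3.1. The sentence may only have been meant to say that nothing follows the 28 days, as footnote a and 8.2.5 do say. Even a site that wrongly closed a participant's participation would still have to report an SAE it learned of and considered reasonably related (8.3.1).

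Most of this stands as an argument about likelihood. It does not make the sentence correct. The limit to 28 days is not in it, and the fallback in 8.3.1 covers only related SAEs that come to the investigator's attention, not AEs in general.

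On the neighbouring passages the reply is also largely right. The lists in 7.1 and 7.2 are both permissive, so one cause may lead to stopping treatment alone or to leaving the study as well, and 7.1 asks sites to document which. A reader might infer that 7.2 flatly contradicts 7.1. The documents show only a tension. The narrower wording in 8.2.5 is a real mismatch but a small one, because that section refers to the Schedule of Activities and expects contact to assess AEs.

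**Conclusion.** The inconsistency is real. One operative sentence in 7.1 is wrong as written, measured against its own next paragraph, the follow-up and collection rules elsewhere, and both analysis windows. It is minor: a site error is unlikely, and the documents do not allow the number of affected participants or lost events to be estimated.

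Three stronger readings are tempting and not supported:

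- **That post-treatment safety data will be lost.** Nothing shows that any site would follow the first sentence over the rest of the protocol.
- **That the number of conflicting provisions measures the harm.** Several of them merely apply the period defined in 8.3.1, and wide agreement on 28 days makes an error less likely.
- **That the sentence is right for consent withdrawal and wrong for every other listed reason.** Sections 7.2.1 and 8.3.1 separate withdrawal from treatment from withdrawal of consent for further contact or future information. Someone who withdraws only from treatment is still followed.

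The conclusion rests on reading the first sentence as it stands, without adding the 28-day limit that its authors may have intended. The 28-day design itself is not in question.

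**What to change.** In Protocol 7.1, delete the sentence saying that the participant does not remain for evaluation, or limit it to evaluation beyond the 28-day safety follow-up.

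In the same edit:

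- In 7.2, cross-refer to the active collection period in 8.3.1 and 8.3.1.2, so that AE/SAE collection after leaving the study follows the limits already stated there. No separate list of exceptions is needed.
- In 8.2.5, use the scope given in footnote a of the Schedule of Activities, which covers any AE or SAE, subject to 8.3.1.2.

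The SAP needs no change on this point, since its window already ends 28 days after the last dose.

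The cost is a clarification letter or a wording amendment. The 28-day contact is already scheduled and may be made by telephone, so no visit is added. No treatment-stopping or dosing rule changes.

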7.2. Participant Discontinuation/Withdrawal From the Study

A participant may withdraw from the study at any time at his/her own request. Reasons for discontinuation from the study may include the following:

- Refused further follow-up;
- Lost to follow-up;
- Death;
- Study terminated by sponsor;
- Progressive Disease;
- Pregnancy;
- Global deterioration of health status;
- Unacceptable toxicity
- Withdrawal of consent;
- Significant noncompliance.

The participant will be permanently discontinued both from the study intervention and from the study at that time.

If a participant withdraws from the study, he/she may request destruction of any remaining samples taken and not tested, and the investigator must document any such requests in the site study records and notify the sponsor accordingly.

If the participant withdraws from the study and also withdraws consent (see [Section 7.2.1](#)) for disclosure of future information, no further evaluations should be performed and no additional data should be collected. The sponsor may retain and continue to use any data collected before such withdrawal of consent.

Lack of completion of all or any of the withdrawal/early termination procedures will not be viewed as protocol deviations so long as the participant's safety was preserved.

7.2.1. Withdrawal of Consent

Participants who request to discontinue receipt of study intervention will remain in the study and must continue to be followed for protocol-specified follow-up procedures. The only exception to this is when a participant specifically withdraws consent for any further contact with him or her or persons previously authorized by the participant to provide this information. Participants should notify the investigator in writing of the decision to withdraw consent from future follow-up, whenever possible. The withdrawal of consent should be explained in detail in the medical records by the investigator, as to whether the withdrawal is only from further receipt of study intervention or also from study procedures and/or posttreatment study follow-up, and entered on the appropriate CRF page. In the event that vital status (whether the participant is alive or dead) is being measured, publicly available information should be used to determine vital status only as appropriately directed in accordance with local law.

7.3. Lost to Follow-up

A participant will be considered lost to follow-up if he or she repeatedly fails to return for scheduled visits and is unable to be contacted by the study site.

The following actions must be taken if a participant fails to return to the clinic for/attend a required study visit:

The site must attempt to contact the participant and reschedule the missed visit as soon as possible and counsel the participant on the importance of maintaining the assigned visit schedule and ascertain whether or not the participant wishes to and/or should continue in the study;

Before a participant is deemed lost to follow-up, the investigator or designee must make every effort to regain contact with the participant (where possible, 3 telephone calls and, if necessary, a certified letter to the participant's last known mailing address or local equivalent methods). These contact attempts should be documented in the participant's medical record;

Should the participant continue to be unreachable, he/she will be considered to have withdrawn from the study.

8. STUDY ASSESSMENTS AND PROCEDURES

The investigator (or an appropriate delegate at the investigator site) must obtain a signed and dated ICD before performing any study-specific procedures.

Study procedures and their timing are summarized in the [SoA](#). Protocol waivers or exemptions are not allowed. Refer to [Appendix 7](#) for alternative measures during the COVID-19 pandemic.

Safety issues should be discussed with the sponsor immediately upon occurrence or awareness to determine whether the participant should continue or discontinue study intervention.

Adherence to the study design requirements, including those specified in the [SoA](#), is essential and required for study conduct.

All screening evaluations must be completed and reviewed to confirm that potential participants meet all eligibility criteria. The investigator will maintain a screening log to record details of all participants screened and to confirm eligibility or record reasons for screening failure, as applicable.

Every effort should be made to ensure that -protocol-required tests and procedures are completed as described. However, it is anticipated that from time to time there may be circumstances outside the control of the investigator that may make it unfeasible to perform the test. In these cases, the investigator must take all steps necessary to ensure the safety and well-being of the participant. When a -protocol-required test cannot be performed, the investigator will document the reason for the missed test and any corrective and preventive actions that he or she has taken to ensure that required processes are adhered to as soon as possible. The study team must be informed of these incidents in a timely manner.

For samples being collected and shipped, detailed collection, processing, storage, and shipment instructions and contact information will be provided to the investigator site prior to initiation of the study.

8.1. Efficacy Assessments

Not applicable.

8.2. Safety Assessments

Planned time points for all safety assessments are provided in the [SoA](#). Unscheduled clinical laboratory measurements may be obtained at any time during the study to assess any perceived safety issues.

8.2.1. Physical Examinations/Vital Signs/ECG

Physical examinations and vital signs will be performed as per standard of care at the Study Center but will not be recorded in the CRF. A finding representing an AE will be recorded in the AE CRF as described in [Section 8.3.1](#).

ECG values of potential clinical concern are listed in [Appendix 6: ECG](#).

8.2.2. Clinical Safety Laboratory Assessments

Timing and frequency of clinical safety laboratory tests are to be performed per standard of care and at any time during the study to assess any perceived safety issues. [Appendix 2](#) includes laboratory tests recommended to determine dosing eligibility.

The investigator must review the laboratory report, document this review, and record any clinically relevant changes occurring during the study in the AE section of the CRF. Clinically significant abnormal laboratory findings are those which are not associated with

the underlying disease, unless judged by the investigator to be more severe than expected for the participant's condition.

All laboratory tests with values considered clinically significantly abnormal during participation in the study or within 28 days after the last dose of study intervention should be repeated until the values return to normal or baseline or are no longer considered clinically significant by the investigator or medical monitor.

If such values do not return to normal/baseline within a period of time judged reasonable by the investigator, the etiology should be identified and the sponsor notified.

See [Appendix 5](#) for suggested actions and follow-up assessments in the event of potential drug-induced liver injury.

8.2.3. Pregnancy Testing

Pregnancy tests may be urine or serum tests, but must have a sensitivity of at least 25 mIU/mL. Pregnancy tests will be performed in WOCBP at the times listed in the [SoA](#). Following a negative pregnancy test result at screening, appropriate contraception must be commenced, and a second negative pregnancy test result will be required at the baseline visit prior the participant's receiving the study intervention/study treatment. Pregnancy tests will also be done whenever 1 menstrual cycle is missed during the active treatment period (or when potential pregnancy is otherwise suspected) and at the end of the study treatment. Pregnancy tests may also be repeated if requested by IRBs/ECs or if required by local regulations. If a urine test cannot be confirmed as negative (eg, an ambiguous result), a serum pregnancy test is required. In such cases, the participant must be excluded if the serum pregnancy result is positive.

8.2.4. Disease Assessment

Imaging and tumor assessments will be conducted per the site's standard of care and will not be recorded in the CRF. A finding representing an AE will be recorded in the AE CRF as described in [Section 8.3.1](#).

8.2.5. One Month Safety Follow-up

For follow-up procedures see [SoA](#) and [Section 8](#).

Study participants will be followed for 28 calendar days after the last administration of study treatment to capture any potential AEs leading to permanent study treatment discontinuation/SAEs.

In the event a participant is unable to return to the clinic for the follow-up visit, telephone contact with the participant to assess AEs and treatment is expected. If laboratory assessments are needed to follow up unresolved AEs, retrieval of assessments performed at an institution local to the participant is acceptable. No further follow-up is required after the 28 day safety reporting period.

8.3. Adverse Events and Serious Adverse Events

The definitions of an AE and an SAE can be found in [Appendix 3](#).

AEs will be reported by the participant (or, when appropriate, by a caregiver, surrogate, or the participant's legally authorized representative).

The investigator and any qualified designees are responsible for detecting, documenting, and recording events that meet the definition of an AE or SAE and remain responsible to pursue and obtain adequate information both to determine the outcome and to assess whether the event meets the criteria for classification as an SAE or caused the participant to discontinue the study intervention (see [Section 7.1](#)).

Each participant/parent/legal guardian/legally authorized representative will be questioned about the occurrence of AEs in a nonleading manner.

In addition, the investigator may be requested by Pfizer Safety to obtain specific follow-up information in an expedited fashion.

